7.2 Study Conduct

7.2.1 Protocol Deviations

Subjects who deviate from protocol conditions (e.g., important inclusion/exclusion criteria) will be reported as having important protocol deviations. Important protocol deviations that are determined to affect the primary efficacy results are deemed Relevant Protocol Deviations. Relevant protocol deviations will be identified for all subjects who are randomized. Relevant Protocol Deviation Criteria are as follows:

- Subject randomized to apixaban group but not dosed with apixaban for > 3 consecutive days (excluding protocol defined interruptions)
- Error in treatment assignment resulting in a subject being dosed with an incorrect treatment for > 3 consecutive days
- Randomized subjects without a functioning CVAD placed between Day -7 and Day 4 \pm 3 of induction chemotherapy
- Randomized subjects with a prior history of documented DVT or PE in the past 3 months
- Randomized subjects with known inherited bleeding disorder or coagulopathy
- Prohibited and/or Restricted Treatments during study period
 - Any anti-platelet therapy with aspirin or thienopyridines such as clopidogrel, ticagrelor, or prasugrel.
 - Concomitant systemic treatment with strong inhibitors of both cytochrome P450 3A4(CYP3A4) and P-glycoprotein (P-gp), such as ketoconazole, itraconazole, posaconazole, telithromycin, clarithromycin, indinavir, nelfinavir, saquinavir, cobicistat, and ritonavir.
 - Concomitant systemic treatment with strong inducers of both cytochrome P450 3A4 (CYP3A4) and P-glycoprotein (P-gp), such as rifampin, carbamazepine, phenytoin and St. John's Wort.
 - Chronic daily use of nonsteroidal anti-inflammatory drugs (NSAIDs, eg, naproxen, ibuprofen, diclofenac) may increase the risk of bleeding. Therefore, concomitant use of NSAIDS more than 7 consecutive days is prohibited.

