Apixaban is hepatically metabolized by cytochrome P-450 3A4 (CYP3A4) and is a substrate for the efflux transporter P-glycoprotein (P-GP). Co-administration of drugs that are strong inhibitors of both CYP3A4 and P-GP can increase apixaban blood concentrations. Patients with renal insufficiency or of low body weight may be at increased risk of excessive anticoagulation due to CYP and P-gp drug interactions, and avoidance of certain drug combinations should be considered.

Examples of strong inhibitors of CYP3A4 are prohibited while subjects are on treatment with BMS-562247. Some examples of strong inhibitors of CYP3A4 are:

Clarithromycin	nelfinavir
telithromycin	ritonavir
itraconazole	saquinavir
ketoconazole	indinavir
voriconazole	cobicistat
posaconazole	

Strong inducers of P-gp and CYP3A4 are expected to decrease apixaban blood concentrations and can result in failure of therapeutic anticoagulant effect.

Examples of strong inducers of both CYP3A4 and P-gp are:

Rifampin	phenytoin
carbamazepine	St. John's wort

These lists are not meant to be all inclusive. Please consult individual drug labels for further information.

Management suggestions:

Avoid co-administration of strong inhibitors of both CYP3A4 and P-gp. Bleeding risk is expected to be further increased in patients with renal insufficiency, depending upon severity.

The efficacy of routine coagulation testing to evaluate the degree of anticoagulation with apixaban is limited.

Avoid co-administration of strong inducers of both CYP34 and P-gp.

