6.3 Populations for Analyses

The following population will be used for the analyses.

Enrolled Population

The Enrolled Subjects population consists of all subjects who signed informed consent.

Randomized /Intent-To-Treat (ITT) Population

The Randomized/Intent-to-treat (ITT) population consists of all subjects who were randomized to a treatment, regardless of whether they received study drug or not. Except as noted otherwise, the ITT Population will be used for evaluation of efficacy.

Modified Intent-To-Treat (mITT) Population

The mITT population includes randomized subjects who have either an adjudicated event making up the primary efficacy endpoint or evaluable end of study imaging evaluations, including ultrasound and echocardiogram

Evaluable Population

The Evaluable population will include the Randomized/ITT population, except those subjects with relevant protocol deviations expected to affect the primary efficacy endpoint.

The relevant protocol deviations, used to determine exclusions, are listed in [Section 7.2](#).

Safety Population

The safety population for safety endpoints includes all randomized subjects, since there is no intervention on top of standard of care in the control arm. Additional analyses will be performed for subjects treated with apixaban.

Pharmacokinetic (PK) Population

The analysis population for pharmacokinetic assessments will include subjects who have received at least one dose of apixaban and have a pharmacokinetic sample collected.

Pharmacodynamics (PD) Population

The analysis population for anti-FXa assessments will include subjects who have received at least one dose of apixaban and have anti-FXa samples collected.

Subgroup Populations

Table 6.3-1 shows the subpopulations of interest for analyses of efficacy and bleeding.

Table 6.3-1: Subgroups of Interest for Efficacy and Bleeding Assessments

Grouping Variable	Subgroups
Geographic region	North America Europe Latin America Asia/Pacific
Age (stratification variable)	< 10 years old ≥10 to < 18 years old
Age category	Young Children 1 year to <2 years Young Children 2 years to 6 years Children 6 years to <12 years Adolescents 12 years to <18 years
Ethnicity	Hispanic/Latino

Table 6.3-1: Subgroups of Interest for Efficacy and Bleeding Assessments

Grouping Variable	Subgroups
	Not Hispanic/Latino
Gender	Male Female
Race	White Black / African American Asian Other
Weight	< 35 kg ≥35 kg

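### SAP 7.2.1 counts prohibited drugs as relevant deviations over an undefined study period with no cut-off at the outcome, so a drug started after a primary event can remove that event from the Evaluable analysis

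*SAP*

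**What the plan says.** SAP 7.2.1 applies its criteria to both arms: "Relevant protocol deviations will be identified for all subjects who are randomized". One criterion is headed "Prohibited and/or Restricted Treatments during study period". Under it stand four drug groups: antiplatelets, "Concomitant systemic treatment with strong inhibitors of both cytochrome P450 3A4(CYP3A4) and P-glycoprotein (P-gp"), "Concomitant systemic treatment with strong inducers of both cytochrome P450 3A4 (CYP3A4) and P-glycoprotein (P-gp"), and NSAIDs for more than 7 consecutive days. None of the four carries a start date, an end date or a condition relative to the endpoint.

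SAP 6.3 defines the Evaluable population as the randomized population "except those subjects with relevant protocol deviations expected to affect the primary efficacy endpoint", and says that the deviations used for exclusion are those listed in Section 7.2. SAP 7.5.1.1 runs the Evaluable analysis only if at least 10% of subjects have a relevant deviation. SAP 6.1 defines four periods (Intended Treatment, Treatment, On-treatment, Follow-up). It does not define a study period.

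Protocol 3.4.1 prohibits the same drugs without naming an arm. Protocol Appendix 10 describes the strong inhibitors as "prohibited while subjects are on treatment with BMS-562247".

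**The concern.** A population meant to test robustness should be defined by what happens before the outcome. Here a child can leave the analysis because of how an event was treated, and the event leaves too. Seizure is a listed CVST symptom in Protocol Appendix 5, CVST is a component of the primary endpoint, and phenytoin is a named inducer in the SAP list. Aspirin given after an event would have the same effect.

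The window may also run past the outcome at its other end. Concomitant medication is still assessed at the Day 35 follow-up (Protocol Table 5.1-2), whereas efficacy is summarized over the Intended Treatment Period, which ends at the Day 29 visit. A listed drug first taken during follow-up can therefore exclude a child whose efficacy period is already over.

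At stake are the composition of the Evaluable analysis, the events it retains, and the count that decides whether it is run.

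**Working it through.** **The text, step by step.**

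1. A child has an adjudicated CVST with seizure and is then given phenytoin.
2. Phenytoin is a named strong inducer in SAP 7.2.1, and the use falls within any ordinary meaning of the study period.
3. SAP 6.3 sends exclusions to the Section 7.2 list, so the child leaves the Evaluable population and the CVST leaves with the child.
4. The drug cannot have contributed to an event that preceded it. Protocol 3.5 also has investigational product discontinued at a thromboembolic event, so after that point there is no continuing apixaban dosing for an inducer or inhibitor to act on.

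**The plan's own figure.** SAP 5 gives 500 subjects randomized 1:1, rates of 17% and 8.5%, and one-sided 0.025. Pooled two-proportion formula: z = (d√n − 1.96√(2p̄q̄)) / √(p₁q₁ + p₂q₂), with d = 0.085, n = 250 and p̄ = 0.1275. This gives (1.344 − 0.925)/0.468 = 0.897, or power 81.5%. The stated power above 80% reproduces. Expected events are 0.17 × 250 = 42.5 and 0.085 × 250 = 21.25.

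**Sensitivity to events lost (assumed range; no usage rate is documented).** Let y be the share of event children who start a listed drug after their event. Then:

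- control rate = 42.5(1 − y)/(250 − 42.5y)
- apixaban rate = 21.25(1 − y)/(250 − 21.25y)

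| y | RR, both arms lose y | RR, control only | RR, apixaban only |
|---|---|---|---|
| 0 | 0.500 | 0.500 | 0.500 |
| 5% | 0.498 | 0.522 | 0.477 |
| 10% | 0.496 | 0.546 | 0.454 |
| 20% | 0.491 | 0.604 | 0.407 |

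Worked entry, control only at 10%: 38.25/245.75 = 15.6%, and 0.085/0.156 = 0.546. That row removes about 4 control events (4.25), so a few children are enough to shift the estimate. Equal losses barely move it. Unequal losses can move it either way.

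**Late starters without an event.** If 10 event-free controls (assumed) start a listed drug after Day 29, the control rate becomes 42.5/240 = 17.7% and RR = 0.085/0.177 = 0.48.

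**Trigger.** 10% of 500 is 50 children. Each post-event or post-Day 29 user is one of those 50.

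**The case against.** **The SAP has a filter.** Relevant deviations are those determined, or expected, to affect primary efficacy, so a post-event drug could be set aside case by case. This stands as an ambiguity only. No procedure is given for that judgement, and SAP 6.3 points to the list as the basis for exclusion. In an open-label trial the rule is better fixed in advance.

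**The route is narrow.** This stands. Anticoagulants come first among the prohibited treatments in Protocol 3.4.1 but are absent from the SAP 7.2.1 list, so treating a VTE with LMWH or heparin excludes nobody. Only the listed drugs matter. Fluconazole is permitted, which narrows the inhibitor group further.

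**A reader might infer more:** that inhibitors and inducers should not count in control children at all, because these drugs act through apixaban levels, and that exclusions will fall mainly on controls because sites have no reason to avoid the drugs there. If 20 controls (and no apixaban children) were excluded and had twice the risk, the control rate would be 42.5/270 = 15.7% and RR 0.54. The documents do not support that premise. Protocol 3.4.1 and the synopsis prohibit these drugs without naming an arm, and Appendix 10 does not say that controls may take them. The SAP can limit a criterion to one arm when it means to, as in "Subject randomized to apixaban group but not dosed with apixaban for > 3 consecutive days".

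Limiting the drug criteria to the apixaban arm would also introduce a bias. Assume k users per arm with relative risk r, the same in both arms. Excluding users from both arms leaves RR at 0.50. Excluding them from the apixaban arm only gives an apixaban rate of 21.25/(250 − k + kr):

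- k = 20, r = 2: 21.25/270 = 7.9%, RR 0.46
- k = 25, r = 2: 21.25/275 = 7.7%, RR 0.45
- k = 25, r = 3: 21.25/300 = 7.1%, RR 0.42

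Each of these favours apixaban.

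**Conclusion.** The point holds as a defect of timing. The prohibited-drug criteria use an undefined period with no cut-off at the primary event or at the end of the efficacy period, so the Evaluable population is conditioned in part on post-outcome treatment. That follows from the wording alone.

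The size does not. The number of children affected cannot be computed from the documents, and the RR range of 0.41 to 0.60 rests on assumed losses of up to 20% of event children in a single arm. With equal losses in both arms RR stays between 0.49 and 0.50.

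The reach is limited. The primary analysis is on the randomized population and is unaffected, and the Evaluable analysis is one of four sensitivity analyses and is conditional on the 10% trigger. The wider inference, that control children should be exempt from the inhibitor and inducer criteria, is not supported. The difference in scope between Protocol 3.4.1 and Appendix 10 is a separate inconsistency to be reconciled, not grounds for a one-sided exclusion.

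**What to change.** In SAP 7.2.1, replace the reference to the study period with use of a listed drug that starts on or after randomization, before the first adjudicated primary event, and before the end of the Intended Treatment Period. Apply it identically in both arms, and use the same definition for the 10% count in SAP 7.5.1.1. Two details should be settled in the same edit: how a drug already in use at randomization is counted, and which date closes the window for a child scanned after the Day 29 visit, since SAP 8.3 admits imaging up to Day 40.

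Separately, reconcile Protocol 3.4.1 and Appendix 10 on whom, and for how long, the inhibitor prohibition covers. Do not restrict the SAP criteria to the apixaban arm.

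The cost is SAP wording and a date comparison in programming, plus a protocol clarification. Protocol 3.4 already requires medications taken after consent to be recorded, so no new type of data is needed.

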3.5 Discontinuation of Subjects from Treatment

Subjects MUST discontinue investigational product (and non-investigational product at the discretion of the investigator) for any of the following reasons:

- Withdrawal of informed consent (subject's or guardian's decision to withdraw for any reason).
- Any clinical adverse event (AE), laboratory abnormality or intercurrent illness which, in the opinion of the investigator, indicates that continued participation in the study is not in the best interest of the subject
- Pregnancy
- Termination of the study by Bristol-Myers Squibb (BMS) / Pfizer
- Loss of ability to freely provide consent through imprisonment or involuntary incarceration for treatment of either a psychiatric or physical (eg, infectious disease) illness
- CVAD is lost before the Day 29 ± 5 end-of-study evaluation due to endpoint related events (eg, VTE, serious bleeding)
- Major bleeding event
- Thromboembolic event such as DVT, PE, CVST or arterial thromboembolic event.

In the case of pregnancy, the investigator must immediately notify the BMS Medical Monitor/designee of this event. In most cases, the study drug will be permanently discontinued in an appropriate manner. If the investigator determines a possible favorable benefit/risk ratio that warrants continuation of study drug, a discussion between the investigator and the BMS Medical Monitor/designee must occur.

All subjects who discontinue study drug (ie, are off protocol therapy), including discontinuation due to thromboembolic or major bleeding event, or loss of catheter before the Day 29 \pm 5 end-of-study evaluation because of achieving a primary endpoint, should comply with protocol specified follow-up procedures as outlined in [Section 5](#). Every attempt should be made to have the study-related radiographic procedures, Ultrasound and Echocardiogram performed within 72 hours of the event regardless of receiving apixaban or not, and the telephone or in-person safety assessment completed on Day 35 \pm 5 Days.

If the catheter is to be removed and replaced within 48 hours due to events other than a primary endpoint event (eg, VTE or major bleeding), the subject should not have the study mandated ultrasound and echocardiogram until Day 29 visit and should continue with the study treatment (for temporary apixaban interruptions related to an invasive procedure, see [Table 4.5.2-1](#)).

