4.5.2 Temporary Treatment Interruptions

During the course of the study, situations might occur in which the investigator considers a temporary interruption of study drug treatment necessary. For example, a lumbar puncture, a planned catheter replacement, a scheduled surgical procedure, occurrence of thrombocytopenia or elevated liver function tests. The treating physician should be informed about timing and dosage of apixaban administration at such circumstances. It is important to let the treating physician know that routine coagulation tests such as INR/PT and aPTT are relatively insensitive measures of activity and therefore may be unsuitable for monitoring. Dose interruptions for selected events are described in the table below (Table 4.5.2-1). For treatment interruptions ≥ 48 consecutive hours, the period of interruption should be noted and the investigator should document on the CRF the time and date of discontinuation and restart of therapy, as well as the reason for discontinuation and measures taken to correct the event, excluding protocol mandated interruptions. An AE/SAE should be reported if applicable. For an individual subject, dose interruptions and treatment discontinuation may be more or less conservative than indicated below in Table 4.5.2-1 based on the clinical judgment of the investigator. Note that discontinuation of subjects from treatment is addressed in Section 3.5

Apixaban should not be administered if the platelet count is $< 20,000$ /microL. A subject may be transfused platelets per investigator's clinical judgement but may not be transfused solely to meet entry criteria.

Note: Once enrolled in the study, decisions to transfuse to maintain platelet counts $\geq 20,000$ /microL or to interrupt study medications should platelet counts fall $< 20,000$ microL is left to the discretion of the clinician as to what is best available care for patients.

Table 4.5.2-1: Temporary Dose Interruptions for Apixaban

Event	Apixaban

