7.4 Extent of Exposure

7.4.1 Study Therapy

Extent of exposure to the study drug is defined as the number of days from first treatment to last treatment (date of last treatment - date of first treatment + 1). Summary of exposure to study drug will show the distribution of the number of days on drug together with the mean days of exposure, for the apixaban treatment group. Additionally, the extent of exposure will be summarized excluding any interruptions.

Treatment compliance (TC) will also be summarized for apixaban treatment group.

For each subject in the apixaban treatment group, treatment compliance (TC) with apixaban is defined as follows.

$$TC = \frac{\text{number of doses taken (tablets or oral solution)}}{(\text{last dose date} - \text{first dose date} + 1 - I) \times 2^{-k+R}} \times 100\%, \text{ where}$$

k=0, if two doses are given on the first day of apixaban

k=1, if one dose is given on the first day of apixaban

R: number of doses needed to be retaken because of the regurgitation, and

I: total number of days study drug was interrupted with a **protocol-defined** interruption.

Regarding protocol-defined interruptions, the number of days from first to last dose of apixaban will exclude the days that subjects have protocol defined dose interruption such as planned lumbar puncture, for conservative side, 2 days will be excluded for one planned lumbar puncture, and 3 days will be excluded for one traumatic lumbar puncture.

Extent of exposure to the study drug will be further tabulated by age stratum.

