7.5.1.1 Sensitivity Analyses for Primary Efficacy Endpoint

In order to assess the robustness of the effectiveness of apixaban relative to standard care, the following sensitivity analyses will be performed for the primary efficacy endpoint:

[figure not shown]
- An analysis will be performed using the mITT Population.

- An analysis will be performed for all randomized subjects with missing primary endpoint or non-evaluable imaging data to be assessed via multiple imputation using 1000 repetitions, with imputation of events for patients with missing data in both treatment groups based on the event rate observed from the corresponding stratum in the standard-of-care arm
- If results from the primary efficacy analysis show a significant difference between treatment groups, then a “tipping point” analysis will be performed with a non-stratified analysis. In each analysis, subjects with missing data in the standard-of-care arm will be assumed to be event-free, while progressively more subjects with missing data in the apixaban arm will be assigned with an event, up to the limit of the number of subjects with missing data in the apixaban arm. The number of subjects in the apixaban arm imputed with event that would change the result from significant to non-significant would be noted.
- An analysis will be performed based on the Evaluable Population, if at least 10% of subjects have a relevant protocol deviation.

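### Read literally, the SAP's undosed-days deviation drops apixaban children who had to stop for an early VTE from the Evaluable sensitivity analysis, while controls with the same event stay in

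*SAP*

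**What the plan says.** Four pieces of text have to be read together.

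- **The mandated stop.** Protocol 3.5 opens with "Subjects MUST discontinue investigational product (and non-investigational product at the discretion of the investigator) for any of the following reasons", and one listed reason is "Thromboembolic event such as DVT, PE, CVST or arterial thromboembolic event". DVT, PE and CVST are components of the primary efficacy endpoint (SAP 4.1).
- **The deviation.** SAP 7.2.1 gives as a relevant deviation: "Subject randomized to apixaban group but not dosed with apixaban for > 3 consecutive days (excluding protocol defined interruptions". The criterion names the apixaban arm only, has no cut-off at the child's event, and states one exemption.
- **The exclusion.** SAP 6.3: "The Evaluable population will include the Randomized/ITT population, except those subjects with relevant protocol deviations expected to affect the primary efficacy endpoint". It adds that "The relevant protocol deviations, used to determine exclusions, are listed in" Section 7.2.
- **The use.** SAP 7.5.1.1: "An analysis will be performed based on the Evaluable Population, if at least 10% of subjects have a relevant protocol deviation". This is one of four sensitivity analyses of the primary endpoint, all introduced as checks of robustness.

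On what counts as an exempt interruption, SAP 7.4.1 refers to "the days that subjects have protocol defined dose interruption such as planned lumbar puncture". Protocol 4.5.2, on temporary interruptions, sends the reader elsewhere for permanent stops: "Note that discontinuation of subjects from treatment is addressed in Section 3.5".

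**The concern.** An apixaban child who has a DVT on, say, Day 15 and stops drug as the protocol requires then has about two weeks without dosing before Day 29. Nothing in the wording of the SAP criterion separates that gap from ordinary non-adherence. The endpoint event itself would therefore cause the child, and the event, to be removed.

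The removal is one-sided. Controls have no dosing criterion. The prohibited-treatment items in SAP 7.2.1 also leave out the first item of Protocol 3.4.1 (LMWH, unfractionated heparin, other oral anticoagulants, systemic tPA). A control who is anticoagulated after a VTE is therefore not removed by that route either.

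Excluding on outcome in one arm lowers that arm's event rate whatever the drug does. An analysis intended to challenge the primary result would instead tend to agree with it.

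**Working it through.** **1. Reproduce the plan's own figure.** Inputs from SAP 5: about 500 randomized 1:1 (250 per arm), 17% versus 8.5%, one-sided 0.025, Pearson chi-square. With pooled rate 0.1275:

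- null SE = √(2 × 0.1275 × 0.8725 / 250) = 0.02983
- alternative SE = √((0.17 × 0.83 + 0.085 × 0.915) / 250) = 0.02959
- z = (0.085 − 1.96 × 0.02983) / 0.02959 ≈ 0.90, so power is 81.5%.

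This agrees with the stated power of more than 80%. The second scenario (200 analysed per arm, 20% versus 10%) gives 80.2%, which also agrees.

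**2. Which events are at risk.** If the last planned dose is on Day 29 and dosing stops after Day D, the undosed days number 29 − D. More than 3 requires D of 25 or earlier. Routine imaging takes place after apixaban has ended (Protocol 5.4.1), so an event first seen there leaves no gap. Only events diagnosed earlier, from symptoms or incidentally, can be lost.

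**3. Effect on the relative risk.** Let p be the true apixaban event rate and f the share of apixaban events diagnosed early enough. Removing those children from numerator and denominator gives

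Evaluable apixaban rate = p(1 − f) / (1 − pf).

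The documents give no value for f, so a range is assumed. The control rate stays at 17%, and no other exclusions are modelled.

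| f | Design rates (p = 8.5%): events removed | Rate | RR | No effect (p = 17%): events removed | Rate | RR |
|---|---|---|---|---|---|---|
| 0 | 0 | 8.50% | 0.50 | 0 | 17.00% | 1.00 |
| 10% | 2.1 of 21.25 | 7.72% | 0.45 | 4.25 of 42.5 | 15.56% | 0.92 |
| 25% | 5.3 | 6.51% | 0.38 | 10.6 | 13.32% | 0.78 |
| 40% | 8.5 | 5.28% | 0.31 | 17.0 | 10.94% | 0.64 |

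Example, f = 25% at design rates: 0.085 × 0.75 / (1 − 0.085 × 0.25) = 0.06375 / 0.97875 = 0.0651, and 0.0651 / 0.17 = 0.38.

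**4. Would the analysis run?** The trigger is 0.10 × 500 = 50 subjects. At the design rate the apixaban arm has 250 × 0.085 = 21.25 events in total, and even with no effect 250 × 0.17 = 42.5. VTE stops alone do not reach 50, so other deviations must make up the rest.

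**The case against.** The best counter-argument is that a mandated stop is compliance. SAP 7.2.1 opens by speaking of subjects who deviate from the protocol, and both it and SAP 6.3 limit relevance to deviations that affect the primary efficacy result. Non-dosing after an event cannot have affected that event. The team might also count gaps only between first and last dose, as SAP 7.4.1 does for compliance. Either reading removes the problem and may well be what is intended. But neither is stated for this criterion. The bullet is the operative rule and carries its own single exemption, so a programmer applying it as written would flag the child.

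Several stronger readings are tempting and not supported:

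- **That the trial's type I error is inflated.** Superiority is concluded from the ITT analysis alone (SAP 7.5.1), and no decision is attached to the Evaluable analysis. A false-positive rate calculated for it would rest on an assumed f and on a simple unstratified test without the 10% trigger, so it would not describe the planned analysis.
- **That liver-rule stops are clearly removed too.** That rule, including its discontinuation step, sits inside Protocol Table 4.5.2-1 on temporary interruptions. Those stops may fall under the exemption, and the SAP's lumbar-puncture example is not presented as exhaustive.
- **That the prohibited-medication items add to the one-sided bias.** They also lack a pre-event cut-off, but they apply to both arms.
- **That every stop required by Protocol 3.5 should be exempt.** That list includes withdrawal of consent and adverse events judged sufficient by the investigator. Exempting all of it would move the Evaluable set back toward ITT.

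**Conclusion.** The point holds for one conditional sensitivity analysis. As written, the criterion can remove apixaban-arm primary events because they occurred, while keeping the same events in controls, and the direction always favours apixaban. The size depends on f, which the documents do not give. Over an assumed 10% to 40%, the Evaluable relative risk is 0.45 to 0.31 where 0.50 is true, and 0.92 to 0.64 where 1.00 is true. These are expected values with 250 per arm and no other exclusions, not a simulation of the planned stratified test.

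The ITT, mITT, multiple-imputation and tipping-point analyses are untouched. Because the benign reading is available, this is a wording gap to close before the deviation programming is fixed. It does not threaten the trial's primary conclusion.

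**What to change.** In SAP 7.2.1, state that non-dosing, or use of a prohibited concomitant medication, counts as a relevant deviation only if it occurs before the child's first adjudicated primary efficacy event. Apply the same cut-off when counting subjects toward the 10% trigger. Do not add a general exemption for Protocol 3.5 discontinuations.

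The cost is one sentence and a date comparison in the deviation programming. No new data are needed, since dosing dates are already recorded (Protocol 4.7) and primary events are adjudicated.

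There are two downsides to record. Slightly fewer children are excluded. Also, children with an event have less time in which to accrue a deviation than event-free apixaban children, whose later gaps still remove them. That second effect should be small, and it works against apixaban.
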